7.4. Unscheduled visits

If a patient returns for an unscheduled visit, following observations and procedures will be completed at a minimum:

- Register visit in IRT
- Physical Exam
- Vital Signs
- 12-lead ECG (only if there is suspicion of cardiac problems)
- Urine pregnancy test (in women of childbearing potential)
- Blood sampling for local lab (hematology, chemistry)
- Infectious disease monitoring (PCR)
- Record concomitant medications
- Record adverse events

Confidentiality Statement

If a patient returns for an unscheduled visit and this visit results in study discontinuation for any reason, the procedures outlined in the End of Study visit (Section 7.3.4.4) should be conducted.

8. ADVERSE EVENT REPORTING

Throughout the study, AEs will be recorded in the source documents and transcribed onto the appropriate pages of the eCRF regardless of whether the AEs are considered treatment related. All AEs with onset dates from signature of the ICF through study exit will be recorded as an AE on the eCRF. All SAEs with onset dates from signature of the ICF through study exit must be recorded following the guidelines in Sections 8.4, 8.6, 8.7, 8.8 and 8.9. Any AE that occurs at any time after completion of the study, which the investigator considers to be related to study drug, must be reported.

Conditions existing prior to screening will be recorded as part of the patient's medical history. To avoid confusion, the AE should be recorded in standard medical terminology. The Investigator is responsible for assessing the relationship of AEs to the AG019 as well as to teplizumab (Section 8.3).

8.1. Adverse Event Definition

An adverse event (AE) is any untoward medical occurrence in a patient administered an investigational product or in whom an investigational product is to be administered, and which does not necessarily have a causal relationship with this treatment. An AE can be any unfavorable and unintended sign (e.g. an abnormal laboratory finding), symptom or disease temporally associated with the use of an investigational product, whether or not considered related to this investigational product. This includes an event that emerges during treatment having been absent pre-treatment or an event that worsens relative to the pre-treatment state ("treatment-emergent adverse event" [TEAE]). Recurrent symptoms of a chronic pre-existing condition are not considered AEs unless they occur in a worse or unexpected pattern during study drug administration.

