5. STUDY TREATMENT

5.1.Treatments

5.1.1AG019

Single dose patients will be treated with (2 or 6 capsules of) AG019.

All patients in the repeat dose cohorts, and all patients in the combination cohorts who are randomized to study treatment, will be treated for 8 weeks with AG019 with one of the doses listed in Table 2:

Table 2: AG019 dosing regimens for repeat dose patients

Dose	Number of capsules	Total daily dose	Treatment duration
Low dose AG019	2 (1 morning, 1 evening)	XXX	8 weeks
High dose AG019	6 (3 morning, 3 evening)	xxx	8 weeks

The total treatment duration for repeat dose patients is 8 weeks or 56 days. Patients will be required to take AG019 for 56 days, even if the Day 56 follow-up visit is not scheduled on Day 56 (there is a 2-day visit window on the Day 56 follow-up visit).

- If the Day 56 follow-up visit is scheduled on Day 54 or Day 55, patients will take their remaining AG019 home again and will continue to take AG019 until the evening dose on Day 56. The patients will then take their remaining AG019 back to the site on Day 90 for final accountability
- If the Day 56 follow-up visit is scheduled on Day 57 or Day 58, patients should be instructed to take AG019 until the evening dose on Day 56.

The daily dose of AG019 to be used in the Phase 2a portion of the study (combination cohorts) is not yet known and will be determined by the results of the Phase 1b portion of the study (AG019 cohorts). Based upon the data obtained in the nonclinical studies, the Sponsor anticipates that a 6-capsule regimen will be administered in the combination cohorts. Following rules will apply:

If the DSMB concludes that no safety concerns are associated with the high dose of AG019 (6 capsules per day) in the Phase 1b portion of the study (AG019 cohorts), the patients enrolled

Confidentiality Statement

in the Phase 2a portion of the study (combination cohorts) will take the high dose of AG019 for 8 weeks.

If the DSMB concludes that safety concerns are associated with the high dose of AG019 (6 capsules per day) in the Phase 1b portion of the study (AG019 cohorts) and that no safety concerns are associated with the low dose of AG019 (2 capsules per day), the DSMB will recommend lowering the AG019 dose in all ongoing and planned (AG019 and) combination cohorts.

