For the randomized patients in the combination cohorts, blinding will be accomplished by arranging for AG019 and placebo components as well as teplizumab and placebo components to have identical packaging. IMP will be delivered in a blinded fashion, as outlined in the Pharmacy Manual. All study personnel at the site, the patient and the Sponsor (except for the clinical supply manager) will be blinded to treatment allocation in the randomized portion of the combination cohorts for the first 6 months of the study. Once all patients in all combination cohorts have completed their 6-month follow-up visit (Day 180), unblinding will be done and all data will be analyzed and reported. After completion of the full 12 months follow-up all additional data will be analyzed and reported separately.

Confidentiality Statement

The identity of IMP assigned to patient numbers or to individual boxes of IMP can be accessed through IRT. When it is medically indicated, the Investigator may contact the MM and Sponsor to discuss the possibility of breaking the blind for a patient. A patient's treatment assignment should only be unblinded when knowledge of the treatment is essential for the further management of the patient (i.e., medical emergency). In the absence of a medical emergency, breaking the code should not be considered.

For emergency blind-break procedures, contact the MM or his/her designee at the contact numbers provided in the Study Manual. The reason and date/time of the unblinding and the name of the individual who broke the blind must be appropriately documented in the patient's medical record or source documents and in the eCRF.

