After all patients in all AG019 and Combination cohorts have completed their 6-month follow-up visit unblinding will be done and all data will be analyzed and reported. After completion of the full 12 months follow-up all additional data will be analyzed and reported separately.

More details on the analysis and presentation of study results will be provided in the statistical analysis plan (SAP). The SAP will be finalized prior to the unblinding of treatment allocation codes.

10.1.Study Endpoints

Primary Endpoint

The primary end point will be assessed by analysis of the incidence of treatment-emergent adverse events (TEAEs) collected up to the 6-month follow-up visit. A TEAE is defined as any event not present prior to the initiation of the treatment(s) or any event already present that worsens in either intensity or frequency following exposure to the treatment(s).

Secondary Endpoints

The pharmacodynamic activity of the study drug(s) will be assessed by measurement of biomarkers in blood and serum samples. Relevant parameters will be assessed, including immune markers for effect, relevant T1D parameters and relevant cytokines. Details about the analysis of the collected PD samples will be described in the SAP.

Following parameters will be assessed for analysis of systemic and local exposure to *L. lactis*:

- Presence of live L. lactis clinical strain bacteria in whole blood
- Measurable serum levels of hIL-10 and hPINS
- Presence of *L. lactis* clinical strain bacteria in fecal excretion

Safety information collected at all other time points will be assessed as secondary end points.

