6.3.8 Adverse Events

AEs will be coded according to the Medical Dictionary for Regulatory Activities (MedDRA) system.

The severity of adverse events will be given in grades 1 to 5 per National Cancer Institute common terminology criteria for adverse events (CTCAE) version 4.0.

All AEs were categorized by the Investigator with respect to their possible relationship to the IMP. The relationship of the AE to AG019, as well as the relationship of the AE to teplizumab, will be assessed separately by the investigator to be not related, unlikely, possible, probable or definite. The categorization:

- reasonably related defined as possible, probable or definite versus
- not reasonably related defined as not related or unlikely will be given in summaries of all adverse events.

If a subject has more than one event with the same preferred term (PT), then the worst severity and the worst relationship will be used.

A TEAE is defined as any adverse event (AE) not present prior to the initiation of the treatment(s) or any AE already present that worsens in either intensity or frequency following exposure to the treatment(s). Hence, events with an onset time at or after the time of treatment start are treatment emergent. Events present at baseline that worsen during the study in either intensity or frequency are also treatment emergent, whereas events present at baseline that become less severe during the study are not. Events that recur during the study are treatment emergent if they recur after complete or partial recovery of the initial event, i.e. should the event first become less severe and then return to its initial severity, it will be considered as a TEAE. AEs reported on the same day as treatment start or after treatment start will be considered TEAEs, as investigators are instructed only to report TEAEs after treatment start.

A Serious Adverse Event (SAE) is defined as any AE occurring at any dose regardless of relationship to IMP that results in any of the following outcomes:

- results in death,
- is life-threatening,
- requires inpatient hospitalisation or prolongation of existing hospitalisation,
- results in persistent or significant disability/incapacity, or
- is a congenital anomaly/birth defect.

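### Protocol 8.1 counts a worse recurrence of a chronic condition as an AE only during dosing, while the primary endpoint counts worsening to Day 180, so such events on Days 57-180 may go unrecorded

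*Protocol*

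**What the plan says.** **Definition used by sites.** Protocol 8.1 defines an AE broadly and includes "an event that worsens relative to the pre-treatment state", with no end date on that clause. The closing sentence of the section then says: "Recurrent symptoms of a chronic pre-existing condition are not considered AEs unless they occur in a worse or unexpected pattern during study drug administration".

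**Length of dosing.** Protocol 5.1.1: "The total treatment duration for repeat dose patients is 8 weeks or 56 days". Combination patients take AG019 or placebo capsules over the same 8 weeks. Their infusions end on Day 12, inside that period.

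**Primary endpoint.** Protocol 10.1 uses the "incidence of treatment-emergent adverse events (TEAEs) collected up to the 6-month follow-up visit". Its TEAE definition covers new events and also "any event already present that worsens in either intensity or frequency following exposure to the treatment(s"). SAP 3.1 repeats this, and SAP 6.3.8 adds: "Events present at baseline that worsen during the study in either intensity or frequency are also treatment emergent". Protocol 5.10 equates the 6-month visit with Day 180.

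**Recording.** The opening of Protocol Section 8 has AEs recorded from consent to study exit and sends conditions that predate screening to medical history. Protocol 8.4 asks for every observed or volunteered complaint to be recorded, whether or not it is linked to treatment.

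**The concern.** The rule that tells a site what is an AE is narrower, for one kind of event, than the rule that tells the analyst what is a TEAE. If a chronic condition flares worse than before in the months after dosing, the last sentence of 8.1 says it is not an AE, while 10.1 and the SAP say it belongs in the primary endpoint.

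The SAP cannot repair this. SAP 6.3.8 treats AEs reported on or after treatment start as TEAEs, on the ground that investigators are told to report only TEAEs from then on. SAP 6.6 analyses data as they stand, apart from missing AE and medication dates. What the site enters therefore decides what is counted.

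Any effect would lower primary TEAE incidence, and it could vary between sites according to which sentence they follow. SAP 6.3.8 also tabulates TEAEs both in total and for the AG019 treatment period alone. Under a literal reading of 8.1, part of the contrast between those tables would reflect the recording rule. The post-dosing months matter here because AG019 is meant to induce long-term tolerance (Protocol 1.1 and 3.4).

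**Working it through.** The plan gives no figure for this point. It does equate 8 weeks with 56 days, and 8 x 7 = 56 confirms that.

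**1. Period in which the clause can apply**

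Inputs: last dosing day 56 (Protocol 5.1.1); end of primary window Day 180 (Protocol 5.10 and 10.1).

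- Days after dosing within the window: 180 - 56 = 124 (Days 57 to 180).
- Share of the window: 124 / 180 = 0.689, or 69%.

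This holds for repeat-dose and combination patients who complete dosing. It does not apply to the single-dose period, where follow-up ends on Day 4.

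**2. The rules applied to example events**

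| Event | 8.1, last sentence | 8.1, preceding sentence | 8.4 | 10.1 / SAP 6.3.8 |
|---|---|---|---|---|
| Worse recurrence of a chronic condition while dosing | AE | AE | record | TEAE |
| Worse recurrence of a chronic condition, e.g. Day 100 | not an AE | AE | record | TEAE |
| New-onset event, e.g. Day 100 | does not apply | AE under the general definition | record | TEAE |

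Only the second row shows a conflict.

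**3. Number of events affected**

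This would need the rate of worsened recurrences after Day 56 and the proportion of sites that follow the last sentence of 8.1. The documents give neither. Protocol 10.2 bases the sample size on no event rate, so the number cannot be computed.

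**4. Effect of the change**

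If the exception in 8.1 ran from first dose onward, the part of the primary window in which the rules disagree would fall from 124 of 180 days to 0 of 180.

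**The case against.** The best defence is that the rest of the protocol points the other way.

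- The preceding sentence of 8.1 already counts worsening against the pre-treatment state.
- Section 8 records AEs to study exit, and 8.4 asks for all complaints.
- AEs are recorded at the Day 90 and Day 180 visits (7.3.4).
- The 8.7 list for SAE reports includes worsening of an observation documented since consent.
- The obvious symptoms of the one chronic condition every patient has are handled separately: level 2-3 hypoglycemia goes on its own eCRF page, and major hyperglycemia is recorded as an SAE (8.4).
- The study is descriptive, with no hypothesis tests.

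Much of this stands, and it narrows the point to one subset of events. It does not remove the conflict. The last sentence of 8.1 is the specific rule for chronic conditions and follows the general one, so a site may reasonably treat it as controlling. Recording AEs to study exit, or at a given visit, still depends on what counts as an AE. Medical history also gives a site another place to enter such a flare.

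Two stronger readings are tempting, and neither is supported. A reader might infer that 8.1 stops counting all worsening of pre-existing conditions after dosing. It does not: the sentence covers recurrent symptoms of chronic conditions only. A reader might also infer that the endpoint is under-recorded for 69% of its window. The 69% is calendar time in which one clause could matter. New-onset events are still captured throughout, and no loss has been shown.

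**Conclusion.** Protocol 8.1 is inconsistent within itself and with 8.4, 10.1 and SAP 3.1 and 6.3.8 for one subset of events: worsened recurrences of chronic pre-existing conditions after dosing ends. Such events on Days 57-180 may go unrecorded in repeat-dose and combination patients, and an event never recorded as an AE cannot enter the primary endpoint. The possible bias is downward and its size is unknown.

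This rests on two assumptions: that at least some sites apply the last sentence of 8.1 literally, and that such recurrences occur. The documents establish neither. The exclusion criteria reduce the number of patients with relevant conditions but do not bring it to zero, since several depend on the investigator's judgement of risk.

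The correction is worth making because it is cheap and the endpoint concerned is the primary one. The documents do not support calling the endpoint compromised.

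**What to change.** 1. In the last sentence of Protocol 8.1, replace the closing words that tie the exception to dosing with: *at any time after the first administration of study drug*. This brings the sentence into line with the TEAE definition in 10.1.
2. Notify sites that a worse or unexpected pattern of a chronic condition is an AE after Day 56 as well.
3. Before the Day 180 unblinding, query worsening after Day 56 of medical-history conditions in repeat-dose and combination patients. SAP 6.9 reports two interim analyses as already done, and Protocol 10.8 unblinds Combination Cohort 1 at the second. If that has happened, note that the queries for that cohort were raised after unblinding.
4. If the query is no longer possible, state in the study report that capture of these events after Day 56 may be incomplete, and say so beside the comparison of total and treatment-period TEAE tables.

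The cost is one amended sentence with the approvals required by Protocol 12.2, a site memo, and some extra AE records and queries.

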8.2. Assessing Severity of Adverse Events

The severity of adverse events will be designated as mild, moderate, severe, life threatening, or fatal per National Cancer Institute (NCI) common terminology criteria for adverse events (CTCAE) version 4.0. If not specifically addressed in NCI CTCAE version 4.0, use the table below:

Mild – Grade 1	Transient or mild discomfort; requiring no limitation of activity; no therapy
Moderate – Grade 2	Mild-moderate impact on activity; requiring some assistance and medical intervention

Confidentiality Statement

Severe – Grade 3	Marked impact on activity; requiring some assistance and medical intervention	
Life Threatening – Grade 4	Complete disability; requiring significant assistance and medical intervention and/or hospitalization	
Death – Grade 5	Adverse event with fatal outcome	

The term "severe" is often used to describe the intensity (severity) of a specific event (as in mild, moderate, or severe myocardial infarction); the event itself, however, may be of relative minor medical significance (such as severe headache). This is not the same as "serious", which is based on patient/event outcome or action criteria usually associated with events that pose a threat to a patient's life or functioning. Seriousness (not severity) serves as a guide for defining regulatory reporting obligations.

8.2.1Grading of Hypoglycemic and Hyperglycemic Events

For this study of participants with type 1 diabetes, the NCI-CTCAE will not be used to grade hypoglycemia and hyperglycemia. Please refer to the grading criteria for hypoglycemic and hyperglycemic events below.

In line with the Joint Position Statement of the American Diabetes Association and the European Association for the Study of Diabetes (International Hypoglycaemia Study, 2017), events of hypoglycemia will be classified as outlined below.

- hypoglycemia Level 1: A glucose alert value of 3.9 mmol/l (70 mg/dl) or less for at least 20 minutes
- hypoglycemia Level 2: A glucose level of <3.0 mmol/l (<54 mg/dl), sufficiently low to indicate serious, clinically important hypoglycemia.
- hypoglycemia Level 3: Severe hypoglycemia, as defined by the American Diabetes Association, denoting severe cognitive impairment requiring external assistance for recovery.

Major hyperglycemic events will be defined and graded as follows:

- Grade 4 = coma or life-threatening event or event resulting in hospitalization.
- Grade 5 = death.

For this study diabetic ketoacidosis (DKA) should be reported as grade 4 hyperglycemia (a single adverse event) resulting in hospitalization and/or life threatening consequences.

Confidentiality Statement

8.3. Assessing Relationship to Study Treatment

All AEs will be categorized by the Investigator with respect to their possible relationship to the IMP. The relationship of the AE to AG019, as well as the relationship of the AE to teplizumab, will be assessed separately by the investigator to be not related, unlikely, possible, probable or definite, as follows:

- Not related: No relationship between the AE and the administration of IMP, judged clearly and incontrovertibly due to extraneous causes (disease, environment etc.).
- Unlikely: The AE is more likely due to an alternative explanation such as concomitant medication(s), concomitant disease(s) and/or the time relationship suggests that a causal relationship is unlikely.
- Possible: The AE might be due to the administration of IMP. An alternative explanation such as concomitant medication(s), concomitant disease(s) is inconclusive. The time relationship is reasonable therefore the causal relationship cannot be excluded.
- Probable: The AE might be due to the administration of IMP. An alternative explanation such as concomitant medication(s), concomitant disease(s) is less likely. The time relationship is suggestive, i.e., it is confirmed by de-challenge.
- Definite: There is no uncertainty in relationship to the administration of IMP. The AE cannot be reasonably explained by an alternative explanation such as concomitant medication(s), concomitant disease(s). The time relationship is very suggestive, i.e. it is confirmed by dechallenge and re-challenge.

"Not related and Unlikely related" correspond to "no reasonable possibility". "Possible, probable and definite" correspond to "reasonable possibility".

8.4. Recording of Adverse Events

All AEs encountered during the clinical study will be recorded in detail in the source documents and documented in the eCRF, from signature of the ICF through study exit. All AEs that meet the seriousness criteria (Section 8.6) should also be recorded on the SAE Report Form. All SAEs must be reported to the sponsor or delegated organization within the timeline stated in Section 8.7.

The recording of AEs will be based on data obtained from the following sources:

- Medical and surgical history
- Physical examinations including vital signs
- Clinical laboratory test results
- Information provided by the patient, either during the follow-up visits or in the patient's diary All clinical events, including both observed (such as any reaction at sites of application) and volunteered problems, complaints, or symptoms, are to be recorded. The need to capture this information is not dependent upon whether the clinical event is associated with the use of any IMP.

If at any time during the study a patient develops symptoms suggesting clinically significant bacteremia that can be attributed to *L. lactis* sAGX0407 (as determined by three consecutive positive blood cultures), study treatment will be discontinued.

A disposition plan for the management of clinical sepsis is provided in Appendix B.

Confidentiality Statement

For the purposes of this study, hypoglycemia events classified as level 1 as defined in Section 8.2.1 will not be recorded separately on the hypoglycemia event eCRF, unless the investigator feels that the event is medically important. Hypoglycemia events level 2 and 3 as defined in Section 8.2.1 will be recorded separately on the hypoglycemia event eCRF. The evaluation that produced the value or result should be repeated until that value or result returns to normal or can be explained and the participant's safety is not at risk. In addition, all hypoglycemia events meeting the definition of SAE as mentioned in Section 8.6, should be recorded as serious adverse events in the eCRF.

Major hyperglycemic events as defined in Section 8.2.1 will be recorded as serious adverse events. In addition, all hyperglycemia events meeting the definition of SAE as mentioned in Section 8.6, should be recorded as serious adverse events. Any other hyperglycemic event (defined as blood glucose >140mg/dL for at least 20 minutes) will not be recorded as adverse event, unless the investigator considers the event to be medically important.

